3.2 Treatment Phase

On the infusion day, patients will be followed according to the assessments schedule in Table 8-1. LysaKare[®] (1,000 mL solution) will be administered intravenously for 4 hours. Before the infusion (at 0 h time point), a set of baseline tests will be performed. During and after the infusion, the patient's condition will be monitored for evaluation of any adverse events.

Patients will have an option to stay overnight in the clinic or can leave after the 12 h assessment and return to the clinic for the 24 h assessments. All patients will be discharged from the unit after the completion of the 24 h assessments.

Only patients with potassium level of ≤ 6 mmol/L at screening will be allowed to be dosed. For Poland only, only patients with potassium level of ≤ 5.5 mmol/L at screening will be allowed to be dosed. Potassium testing on the infusion day will be performed at 0 h (before the infusion), at 2 h (during the infusion) and 4 h, 6 h, 8 h, 12 h, and 24 h (after the infusion). Vital signs and ECGs will be taken as specified in the assessment schedule.

All patients will be monitored closely for signs and symptoms of hyperkalemia, e.g. dyspnoea, weakness, numbness, chest pain and cardiac manifestations (conduction abnormalities and cardiac arrhythmias).

Patients should be instructed to drink substantial quantities of water (at least 1 glass every hour) on the day of infusion to remain hydrated and facilitate excretion of excess serum potassium. Patients are permitted to void as needed.

In case of signs and symptoms of hyperkalaemia, LysaKare[®] infusion must be stopped and appropriate corrective measures must be taken. In the occurrence of severe renal insufficiency referral to hemodialysis unit should be considered per investigator discretion.

Advanced Accelerator Applications Clinical Trial Protocol (Version 01)

Confidential

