4.3 Risks and benefits

Amino acid solutions with similar composition to LysaKare[®] have been widely used for renal protection during PRRT treatment.

The evaluation of potential risks of LysaKare[®] for this study is based on the literature data presented in the well-established use application. The LysaKare[®] IB (Guidance to the Investigator) summarizes potential risks and key risk management activities to consider when administering LysaKare[®]. The main adverse reactions reported after the amino acid solution administration include nausea, vomiting and hyperkalemia.

• Nausea and vomiting

The main adverse reactions are nausea (approximately 25%) and vomiting (approximately 10%). Pre-treatment with an antiemetic 30 minutes prior to start of LysaKare[®] infusion is recommended to reduce the incidence of nausea and vomiting.

Hyperkalemia

An increase of serum potassium levels may occur. Serum potassium level increases are generally mild and transient. Vital signs should be monitored during the infusion regardless of baseline serum potassium levels. Patients should be instructed to drink substantial quantities of water (at least 1 glass every hour) on the day of infusion to remain hydrated and facilitate excretion of excess serum potassium. In case hyperkalemia symptoms develop during LysaKare[®] infusion, appropriate corrective measures must be taken. In the occurrence of severe renal insufficiency referral to hemodialysis unit should be considered per investigator discretion.

Safety effects of LysaKare[®] will be carefully assessed in this study, and patients will be closely monitored.

As LysaKare[®] is administered in medical practice with Lutathera[®] as a kidney radiation protection agent and it does not have a therapeutic effect on GEP-NET itself, there is no direct benefit to the patients participating in the study. However, this study will be essential in better understanding the effect of LysaKare[®] on serum potassium levels in the GEP-NET patient population for its safe use with Lutathera[®].

Advanced Accelerator Applications Clinical Trial Protocol (Version 01)

Confidential

5 **Population**

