6.3.2 Dose discontinuation

If a patient discontinues the LysaKare[®] infusion prior to receiving at least 900 mL of LysaKare[®] they should continue with the assessments as outlined in Table 8-1. In case hyperkalemia associated symptoms develop during LysaKare[®] infusion, appropriate corrective measures must be taken per standard of care and physician judgment. Discontinuation of LysaKare[®] infusion should be considered in cases of hyperkalemia related safety concerns as judged by the investigator. In case of severe symptomatic hyperkalemia, the LysaKare[®] infusion should be stopped. In the occurrence of severe renal insufficiency referral to hemodialysis unit should be considered per investigator discretion.

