9.1 Discontinuation

9.1.1 Discontinuation of study treatment

Discontinuation of study treatment for a subject is defined as a situation when study treatment infusion is stopped earlier than the protocol planned duration of 4 h \pm 20 minutes.

The investigator must discontinue study treatment for a given subject if, he/she believes that continuation would negatively impact the subject's well-being or result in a safety risk to the subject.

If discontinuation of study treatment occurs based on the subject's decision, the investigator should make a reasonable effort to understand the primary reason for the subject's premature discontinuation of study treatment and record this information.

Subjects who discontinue study treatment or who decide they do not wish to participate in the study further should NOT be considered withdrawn from the study UNLESS they withdraw their consent. Where possible, they should complete all assessments indicated in the assessment schedule for the infusion day. If subjects fail to return for these assessments for unknown reasons, every effort should be made to contact the subject.

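### Protocol 3.2 requires the infusion to be stopped for any signs and symptoms of hyperkalaemia, 6.3.2 leaves non-severe cases to investigator judgement, and nothing reconciles the two

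*Protocol*

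**What the plan says.** Protocol 3.2 (Treatment Phase) gives the rule for the infusion day: "In case of signs and symptoms of hyperkalaemia, LysaKare[®] infusion must be stopped and appropriate corrective measures must be taken". The synopsis carries the same sentence. Neither place attaches a severity condition. The events to watch for are described in 3.2 as "signs and symptoms of hyperkalemia, e.g. dyspnoea, weakness, numbness, chest pain and cardiac manifestations", a list that includes complaints which can be mild.

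Protocol 6.3.2 (Dose discontinuation) treats the same situation in three steps:

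- For symptoms: "In case hyperkalemia associated symptoms develop during LysaKare[®] infusion, appropriate corrective measures must be taken per standard of care and physician judgment".
- For a wider group: "Discontinuation of LysaKare[®] infusion should be considered in cases of hyperkalemia related safety concerns as judged by the investigator".
- For the worst cases: "In case of severe symptomatic hyperkalemia, the LysaKare[®] infusion should be stopped".

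Protocol 4.3 (Risks and benefits) says: "In case hyperkalemia symptoms develop during LysaKare[®] infusion, appropriate corrective measures must be taken". It does not mention stopping.

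Protocol 9.1.1 adds a general duty: "The investigator must discontinue study treatment for a given subject if, he/she believes that continuation would negatively impact" the patient's well-being, or would create a safety risk. It does not mention hyperkalaemia.

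**The concern.** Section 3.2 removes discretion once signs or symptoms appear. Section 6.3.2 restores it for everything short of severe symptomatic hyperkalaemia, and even for severe cases it uses *should* where 3.2 uses *must*. Staff who work from 6.3.2 could in good faith continue an infusion that 3.2 requires them to stop. The same decision would then comply with one section and deviate from another.

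What is at stake is mainly patient safety. The study exists to measure the potassium effect of this infusion, hyperkalaemia is the only adverse event of special interest (SAP 2.7.1.1), and patients have no direct benefit from taking part (Protocol 4.3). A secondary matter is uniform conduct. The SAP reports adverse events leading to discontinuation or interruption (2.7.1) and gives exact 95% confidence intervals for dose interruption or withdrawal (5.4.2). If sites follow different rules, those proportions partly reflect which section a site followed.

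**Working it through.** No calculation underlies the rule, so the check is a comparison of the instructions, followed by one subtraction for reach.

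**Step 1. Instructions side by side, by type of patient during the infusion.**

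| Patient | Synopsis and 3.2 | 6.3.2 | 4.3 | 9.1.1 |
|---|---|---|---|---|
| Severe symptoms | Stop (*must*) | Stop (*should*) | Corrective measures; silent on stopping | Stop if investigator sees harm or risk |
| Non-severe symptoms, investigator sees a safety concern | Stop (*must*) | Consider discontinuing; corrective measures | As above | Stop if investigator sees harm or risk |
| Non-severe symptoms, investigator sees no risk | Stop (*must*) | Corrective measures; no stop directed | As above | No duty arises |

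In the first two rows the practical outcome can converge, through 6.3.2 itself or through 9.1.1. The third row is the gap: 3.2 mandates a stop and nothing in 6.3.2 or 9.1.1 does.

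**Step 2. Can the texts be read together?**

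- *Is 6.3.2 just a restatement of 3.2?* No. If any symptom already required a stop, a separate sentence for severe symptoms would have no work to do. Its presence implies that lesser symptoms are handled differently.
- *Does a stop in 3.2 mean a pause, with discontinuation a later decision?* The terms do not separate that way. Section 6.3.2 uses stopping for its severe tier, and 9.1.1 says: "Discontinuation of study treatment for a subject is defined as a situation when study treatment infusion is stopped earlier than the protocol planned duration".
- *Does 9.1.1 supply the missing stop?* Only when the investigator believes continuing would be harmful or unsafe. The stop in 3.2 has no such condition.
- *Is one of the texts superseded?* No. The change list for Amendment 01 adds the same sentence on haemodialysis referral to 3.2, 4.3 and 6.3.2. All three are current, and the difference on stopping remained.
- *Is there an order of precedence?* None is stated in either document.

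**Step 3. Reach.** Inputs: a target of about 45 patients (synopsis; Protocol 3) and 30 enrolled and infused as of 08 November 2022 (Amendment 01 rationale).

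Patients still to be dosed ≈ 45 − 30 = 15.

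This is a rough figure. The target is approximate, 9.1.2 allows replacements, and the count predates version 01 of 01 December 2022. Only those among the remaining patients who develop non-severe signs or symptoms during the infusion are affected, and the documents give no frequency for that.

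**The case against.** The best reply is that the instructions are cumulative. Under Protocol 13.2 the investigator agrees to follow every instruction in the protocol. A site that stops the infusion complies with all sections, because neither 4.3 nor 6.3.2 expressly permits continuing. On that view the weaker wording is untidy drafting. It is true that all sections can be obeyed at once by stopping. But a general duty to follow everything does not tell a reader of 6.3.2 that its graded scheme is overridden elsewhere, and the separate severe tier points the other way.

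A second reply is that the documents do not show which rule the sponsor intends. Section 4.3 refers to the Investigator's Brochure for risk management, and that is not available here. This stands in part: the text alone cannot prove intent. What favours the 3.2 rule is that it is unconditional, appears twice, sits in the section governing the infusion day, and is the more protective.

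Some stronger readings are tempting and should be set aside:

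- *That 6.3.2 offers only corrective measures for non-severe symptoms.* It also has discontinuation to be considered on investigator judgement.
- *That the protocol divides two places against two.* The synopsis repeats 3.2, and 4.3 is a risk summary in the rationale chapter. Silence there is not a competing rule. The conflict is between 3.2 and 6.3.2.
- *That 15 is a ceiling on the patients affected.* Step 3 of the working shows why it is not.

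**Conclusion.** The inconsistency is real and confined to one group: patients with non-severe signs or symptoms of hyperkalaemia during the infusion whom the investigator does not judge to be at risk. It is worth correcting because the fix is cheap and the matter is the study's central safety concern.

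The exposure is limited. Patients are in clinic and closely monitored, corrective measures are compulsory wherever symptoms during the infusion are addressed, and 9.1.1 requires discontinuation when the investigator sees a safety risk.

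A reader might infer that the primary result is biased. The documents do not support that. The primary estimand disregards discontinuation and interruption (Protocol 12.4.1; SAP 1.2.1), and 6.3.2 keeps patients who stop before 900 mL in the assessment schedule.

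The conclusion rests on the wording of version 01 alone. It assumes that no site instruction outside these documents already settles the point.

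**What to change.** In Protocol 6.3.2, replace the symptom sentence with the rule in 3.2: signs and symptoms of hyperkalaemia require the infusion to be stopped and corrective measures to be taken, the measures following standard of care and physician judgement. Delete the severe-symptom sentence, which the rule then covers. Keep the investigator-judgement sentence for hyperkalaemia-related safety concerns without signs or symptoms. It should not be narrowed further, for example to laboratory findings only, because harmonising the sections does not need that. Add the stop to 4.3 for consistency. Notify sites.

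If the sponsor does intend the graded scheme, the synopsis and 3.2 would have to change instead. Either way, one rule should be stated throughout.

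Cost: a written amendment approved by the sponsor, the IRB/IEC and, where required, health authorities (Protocol 14.1), plus a site notice. No procedure, sample or analysis is added. The downside is that a few more infusions may be stopped early, so some additional patients may fall short of the 900 mL compliance threshold in 6.3.1.

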3.3 Follow-up Phase

After the infusion is complete and the 24-hour sample has been collected the patient will be discharged from the clinic. The investigator will follow-up with the patient via telephone 48-hours after the start of infusion to confirm if the patient experienced any additional adverse events.

If needed, additional visits or assessments (for example, to follow up on adverse events) may be conducted using the Investigator's clinical judgment.

3.4 End of Study

The end of study will occur when the last enrolled patient has completed the follow-up phone contact 48 h after LysaKare[®] infusion.

Advanced Accelerator Applications Clinical Trial Protocol (Version 01)

Confidential

Page | 25 Protocol No.CAAA001A12401

4 Rationale

4.1 Rationale for study design

This is a category 3 Post-Authorization Safety Study (PASS) following the European Medicines Agency (EMA) marketing authorization of LysaKare[®] 25 g/ 15 g solution for infusion. LysaKare[®] is indicated for reduction of renal radiation exposure during peptide-receptor radionuclide therapy (PRRT) with lutetium (177Lu) oxodotreotide in adults. The marketing authorization was granted based on literature data from similar amino acids solutions (well established use application).

The purpose of the study is to evaluate the effect of LysaKare[®] administration on serum potassium levels.

The primary endpoint of this study is the change in serum potassium levels after LysaKare[®] IV administration compared to baseline. The selection of this endpoint is supported by findings of a study, which assessed hourly potassium changes (at 0, 0.5, 1, 2, 4 and 5 hours) measured in 11 patients treated with 2.5% Lys-Arg solution (Krenning 2000). Peak serum potassium levels were observed at 2-4 h post-baseline, the mean baseline level was 4.2 mmol/L, mean increase at 2 h was 0.6 mmol/L and at 4 h it was 0.9 mmol/L (SD=0.3) the maximum increase was 1.5 mmol/L. The mild increase in potassium levels did not manifest in any safety issues or clinically significant events.

The study has a descriptive nature, and no hypothesis will be tested for the study endpoints. The study will describe and analyze various parameters related to potassium concentration, including mean change, maximum change, time to the maximum change, and the overall dynamics of the concentration curve during and after the LysaKare[®] infusion. In order to calculate the sample size for the study, it was assumed that the mean change in potassium levels over baseline values is less than 1.1 mmol/L (a safety margin of 0.2 mmol/L has been added to the mean increase of 0.9 mmol/L observed in the previous study at 4 h).

AA solutions have fast plasma elimination kinetics with AA levels returning to baseline by 6 hours post-dose (Tangphao 1999, Irving 1986). Serum potassium levels after amino acid administration normally return to near baseline within 24 hours (Giovacchini 2011, Lapa 2014a, Lapa 2014b, Krenning 2000). Therefore, the time points for potassium level assessments in this study extend from 0 h to 24 h, and the follow up is conducted at 48 hours post dose.

The study design and patient population mimic the real-world LysaKare[®] administration practice in GEP-NET patients who receive amino acid infusion concomitantly with PRRT (Lutathera[®]). Patient selection thus reflects the indications as well as contraindications and warnings and precautions as outlined in the Lutathera[®] and LysaKare[®] labels.

4.2 Rationale for dose/regimen and duration of treatment

A standard approved dose of LysaKare[®] will be administered to all patients as a 4-hour infusion, as in the real-world practice and according to the EU SmPC. Potassium levels and any clinical manifestations of hyperkalemia will be assessed following the infusion at predefined time points.

Advanced Accelerator Applications Clinical Trial Protocol (Version 01)

Confidential

The study does not evaluate concomitant administration of LysaKare[®] with PRRT (Lutathera[®]) as it is operationally very difficult to collect and analyze radioactive blood samples. From mechanism of action perspective, somatostatin receptor 2 directed PRRT treatment with Lutathera[®] does not lead to increase of serum potassium levels. The hyperkalaemia observed during PRRT treatment is only related to concomitant administration of AA solution, before and during PRRT treatment. The administration of LysaKare[®] without PRRT in this study will confirm the safety profile that is related only to LysaKare[®], without being confounded by side effects of the treatment with Lutathera[®].

4.3 Risks and benefits

Amino acid solutions with similar composition to LysaKare[®] have been widely used for renal protection during PRRT treatment.

The evaluation of potential risks of LysaKare[®] for this study is based on the literature data presented in the well-established use application. The LysaKare[®] IB (Guidance to the Investigator) summarizes potential risks and key risk management activities to consider when administering LysaKare[®]. The main adverse reactions reported after the amino acid solution administration include nausea, vomiting and hyperkalemia.

• Nausea and vomiting

The main adverse reactions are nausea (approximately 25%) and vomiting (approximately 10%). Pre-treatment with an antiemetic 30 minutes prior to start of LysaKare[®] infusion is recommended to reduce the incidence of nausea and vomiting.

Hyperkalemia

An increase of serum potassium levels may occur. Serum potassium level increases are generally mild and transient. Vital signs should be monitored during the infusion regardless of baseline serum potassium levels. Patients should be instructed to drink substantial quantities of water (at least 1 glass every hour) on the day of infusion to remain hydrated and facilitate excretion of excess serum potassium. In case hyperkalemia symptoms develop during LysaKare[®] infusion, appropriate corrective measures must be taken. In the occurrence of severe renal insufficiency referral to hemodialysis unit should be considered per investigator discretion.

Safety effects of LysaKare[®] will be carefully assessed in this study, and patients will be closely monitored.

As LysaKare[®] is administered in medical practice with Lutathera[®] as a kidney radiation protection agent and it does not have a therapeutic effect on GEP-NET itself, there is no direct benefit to the patients participating in the study. However, this study will be essential in better understanding the effect of LysaKare[®] on serum potassium levels in the GEP-NET patient population for its safe use with Lutathera[®].

Advanced Accelerator Applications Clinical Trial Protocol (Version 01)

Confidential

5 **Population**

5.1 Inclusion criteria

Subjects eligible for inclusion in this study must meet **all** of the following criteria:

- 1. Male or female patients with somatostatin receptor positive gastroenteropancreatic neuroendocrine tumor (GEP-NETs), who are eligible for the treatment with Lutathera[®] as per Lutathera[®] label indication.
- 2. Patients ≥ 18 years of age at screening.
- 3. Patients who have provided a signed informed consent form to participate in the study, obtained prior to the start of any protocol related activities.

5.2 Exclusion criteria

Subjects meeting any of the following criteria are not eligible for inclusion in this study.

- 1. Pre-existing hyperkalemia (>6.0 mmol/L at screening) if not adequately corrected before starting the LysaKare[®] infusion. For Poland only, pre-existing hyperkalemia (> 5.5 mmol/L at screening) if not adequately corrected before starting the LysaKare[®] infusion.
- 2. Instances when Lutathera[®] is not recommended per the Lutathera[®] SmPC:
 - a. Uncontrolled congestive heart failure (NYHA III, IV);
 - b. Kidney failure with creatinine clearance < 50 mL/min calculated by the Cockcroft Gault method;
 - c. Impaired haematological function with either Hb < 4.9 mmol/L (8 g/dL), platelets < 75 G/L (75x10³/mm³), or leucocytes < 2 G/L (2,000/mm³) (except lymphopenia);
 - d. Liver impairment with either total bilirubinemia > 3 times the upper limit of normal or albuminemia < 30 g/L and prothrombin ratio decreased < 70%.
- 3. Pregnancy or lactation, positive pregnancy test at screening or pre-dose based on the contraindication for Lutathera[®].
- 4. Hypersensitivity to the IMP active substances.
- 5. Any significant medical or social condition which may interfere with the subject's ability to comply with the study visit schedule or the study assessments.
- 6. Patients who have received any investigational agent within the last 30 days.
- 7. Patients that have received a dose of Lutathera[®] prior to the screening visit or are scheduled for Peptide Receptor Repeat (PRRT) treatment within 7 days of the study infusion of LysaKare[®].

Advanced Accelerator Applications Clinical Trial Protocol (Version 01)

Confidential

6 Treatment

In this study, approximately 45 patients (to have at least 25 patients evaluable for the primary endpoint) diagnosed with GEP-NET that meet the criteria for treatment with Lutathera[®] will be enrolled and receive an infusion with LysaKare[®].

The LysaKare[®] solution will be provided by the Sponsor. Amino acid solutions compounded at the hospital pharmacy are not permitted in this trial.

After the study, treatment with PRRT is only permitted after at least 7 days have elapsed from the LysaKare[®] infusion. The PRRT will not be provided by the Sponsor.

